2.0 Specific Objectives

Objective 1: To characterize clinical outcomes, quality of life and functional impairment over two (2) years in a population of ambulatory patients on evidence-based therapy with advanced chronic systolic heart failure who may benefit from VAD therapy

- Characterize ambulatory patients with advanced heart failure at study entry, including measures of functional capacity and (baseline peak VO₂ and serial 6 minute walk test distance), frailty, biomarkers, and quality of life, and interest in VAD therapy.
- Characterize clinical outcomes of these heart failure subjects over two (2) years of follow-up, including a) hospitalizations, Mechanical Circulatory Support Device (MCSD) implant, heart transplant, survival without MCSD or transplant; survival without MCSD, transplant or substantially impaired health utility and b) functional capacity and quality of life.
- Develop improved risk prediction tools for use in this spectrum of advanced ambulatory chronic systolic heart failure.
- Determine if a second early assessment (at two months) of clinical information provides prognostic value that is additive to that of an initial assessment alone.
- Investigate the test performance characteristics of existing classification systems to determine: a) consistency of associated clinical characteristics of a given profile within

and between sites; b) performance metrics such as calibration, discrimination and accuracy; and c) prognostic ability with respect to clinical outcomes over time.

Objective 2: To evaluate the relationship between heart failure subject's modeled prognosis, self assessed prognosis, preferences for end of life care and thresholds for considering VAD implant.

Objective 3: To evaluate caregiver burden associated with heart failure subject's measures of heart failure severity, quality of life, functional limitations and with preferences for care and thresholds for considering device implant.

- Caregiver burden will be assessed at baseline B and again at 6 months, 1 year, 18 months and 2 years to explore its global trajectory, and as a function of each subject's heart failure severity, quality of life and functional limitations, and the caregiver's health status.
- Patient preferences for care and thresholds for considering device implant will be assessed as a function of caregiver burden.

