Model assumptions will be thoroughly checked using informal (e.g., inspection of residuals) and formal methods (e.g., score test for extra parameters or methods based on likelihood displacement). If individual outliers are detected, their influence will be evaluated using influence diagnostics methods based on comparing estimates from models fitted to data with and without outlying values. Whenever we are not successful in fitting the parametric models (linear or non-linear), then non-parametric analyses and/or transformation of the variables involved in the analysis will be considered.

Two-sided testing will be conducted using a nominal significance level of 0.05 for all tests. No adjustments for multiplicity will be applied. Further details of the analyses will be documented in the Statistical Analysis Plan.

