8.2 Sample Size Considerations

The sample size for this prospective cohort (registry) study is based primarily on logistical considerations. It is anticipated that 400 eligible subjects will be enrolled in the study in the 12-month recruitment period. We predict that 30% of the 400 enrolled participants will achieve clinical outcomes such as death or VAD, or will drop-out during the 2-year study follow-up. Thus, we project that 280 participants will provide year 2 data and we provide the degree of precision with which we can estimate the important clinical outcomes using the conservative estimate of 280 registry participants. A sample of 280 participants will provide precision (half-width of a 95% confidence interval, based on normal approximation; East v6.3; Cytel Inc., 2014) ranging from 2.6% to 5.9% for true incidence rates ranging from 5% to 50% (where precision is minimal), respectively. Figure 3 below shows the correspondence of precision and true proportion of participants. The precision of estimation is improved with the use of time-to-event methods instead of the simpler binomial approach used in the calculations above.

Figure 3: Correspondence of precision and true proportion of participants experiencing clinical outcomes in the 2-year study period for sample size of 280 participants.

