8.3.3 Modeling of Clinical Outcomes

We seek to estimate the morbidity and mortality rates in this population and to evaluate the effectiveness of baseline factors in determining their prognosis. To accomplish this goal [objective 1], we will use logistic regression for dichotomous outcomes (e.g., proportion of subjects with an interest in VAD therapy), Poisson regression for count outcomes (e.g., number of hospitalizations per participant), Cox proportional hazard models for time-to-event outcomes (e.g., survival, time to VAD implantation) and linear mixed-effects models for continuous outcomes (e.g., quality of life, functional capacity)^[30-32]. For time-to-event outcomes, survival time will be defined as the time from consent to the event or, for participants who did not experience an event, to the last study visit. Given the potentially small number of events, differences between groups will be tested by means of the log rank test. For longitudinal continuous outcomes, we will model correlated errors with a first order autoregressive (AR1) process since it is reasonable to assume adjacent values are more correlated than observations father apart in time. Alternative variance-covariance structures will be investigated, if needed.

Univariable models will be developed first, using baseline characteristics as the predictors. Multivariable models will be built incorporating known prognostic factors (i.e., those identified in the literature) and those suggested from the univariable analyses (i.e., those with p<0.10). Given the sample size and the potential for small numbers of events (in time-to-event outcomes), we will apply the principle of parsimony to the number of potential prognostic factors included in the ultimate model. In addition to using such standard methods to develop multivariable risk prediction models, we will derive simplified scoring systems to aid in clinical decision-making. Alternative classification schemes (e.g., CART) will be employed as sensitivity analyses. To assess the performance of the risk prediction models, we will evaluate their calibration (or reliability) discrimination and accuracy^[33].

Comparison among existing classification systems and the use of second early assessments (baseline B measures instead of baseline A measures) with the improved risk prediction model(s) developed above will be based on the concordance index, parsimony of the model, and the other performance metrics described above^[34].

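### Section 8.3.3 compares a risk model selected and fitted in this cohort with existing systems by c-index and states no optimism correction, which favours the new model on average

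*Protocol*

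**What the plan says.** One aim under Objective 1 (Section 2.0) is to "Develop improved risk prediction tools for use in this spectrum of advanced ambulatory chronic systolic heart failure". Section 8.3.3 sets out how:

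- Univariable models on baseline characteristics come first. The multivariable model then takes factors known from the literature and "those suggested from the univariable analyses (i.e., those with p<0.10").
- Because events may be few, parsimony is to limit the number of predictors. No number is set.
- Simplified scores are derived from the models. CART is a sensitivity analysis.
- The new models are assessed for calibration, discrimination and accuracy.
- The comparison of existing systems, and of baseline B with baseline A measures, "with the improved risk prediction model(s) developed above will be based on the concordance index, parsimony of the model" and the same performance metrics.

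On numbers, Section 8.2 says: "It is anticipated that 400 eligible subjects will be enrolled in the study in the 12-month recruitment period", and "We predict that 30% of the 400 enrolled participants will achieve clinical outcomes such as death or VAD, or will drop-out" over two years. Section 8.1 leaves further analysis details to the SAP. The protocol does not mention a split sample, an external cohort, cross-validation, bootstrap or shrinkage for the new models.

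**The concern.** A model whose predictors were picked and whose coefficients were estimated in a data set ranks the patients of that data set better than it ranks new ones. SHFM and HFSS are calculated by the coordinating centre from published formulas (Sections 4.12 and 4.13), so their c-index here carries no such inflation. Setting an uncorrected c-index for the new model beside theirs is an uneven comparison, and apparent calibration in the fitting data is flattering for the same reason.

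At stake is the claim that the registry has produced a better tool. Section 1.1 names improved prognostic assessment as the broader goal and selection of candidates for a future early-LVAD trial as a targeted goal. Section 8.3.3 intends the simplified scores for clinical decision-making. An apparent c-index gain of a few hundredths could be taken as an advance when the tool is no better than the score it replaces.

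**Working it through.** **1. The plan's own figures.** 400 × (1 − 0.30) = 280, matching "we project that 280 participants will provide year 2 data". The 95% half-width is 1.96 × √(p(1 − p)/280). At p = 0.05 this is 1.96 × √(0.0475/280) = 2.55%. At p = 0.50 it is 1.96 × √(0.25/280) = 5.86%. Both agree with "ranging from 2.6% to 5.9% for true incidence rates ranging from 5% to 50"%. These figures concern the precision of a proportion. The protocol gives no figure for the performance of a prediction model.

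**2. Events available.** 0.30 × 400 = 120 is the most that the projection allows for outcomes that end follow-up, such as death or VAD. The 30% includes dropout, so the true count is lower. Hospitalisations are not in this figure. A model for an outcome that includes them could have more events and less optimism.

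**3. Candidates.** No count is given. Section 4.17 alone lists about 13 likely biomarkers and a panel of 10 polymorphisms (13 + 10 = 23). Echocardiographic, exercise, laboratory, frailty and questionnaire measures come on top.

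**4. Simulation.** The inputs taken from the plan are n = 400, two-year follow-up, a Cox model and the p<0.10 screen. The following are assumptions:

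- 40, 80 or 120 events
- 10, 20 or 40 candidates, all pure noise
- one existing score that carries all the true signal (log hazard ratio 0.6 per SD, true c about 0.66)

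Noise candidates passing the screen join the existing score and the model is refitted. The c-index is computed in the same 400 patients and in 1,500 independent ones, with 150 replicates per row.

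| Events | Candidates | c, existing (same data) | c, new (same data) | Apparent gain | Gain in new patients | Share of replicates with new model ahead in same data |
|---|---|---|---|---|---|---|
| 40 | 10 | 0.660 | 0.684 | +0.025 | −0.021 | 0.71 |
| 40 | 20 | 0.659 | 0.700 | +0.041 | −0.034 | 0.88 |
| 40 | 40 | 0.667 | 0.737 | +0.070 | −0.051 | 0.98 |
| 80 | 10 | 0.662 | 0.673 | +0.011 | −0.010 | 0.65 |
| 80 | 20 | 0.661 | 0.684 | +0.023 | −0.020 | 0.86 |
| 80 | 40 | 0.660 | 0.701 | +0.041 | −0.033 | 0.97 |
| 120 | 10 | 0.661 | 0.668 | +0.007 | −0.006 | 0.57 |
| 120 | 20 | 0.659 | 0.674 | +0.015 | −0.013 | 0.88 |
| 120 | 40 | 0.659 | 0.689 | +0.030 | −0.026 | 0.99 |

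**5. Reading one row.** With 80 events and 20 candidates, about 0.10 × 20 = 2 noise predictors should pass the screen, and 2.1 did on average. The new model's c falls from 0.684 in the same data to 0.642 in new patients, an optimism of 0.042. The existing score stays at 0.661 in both. The whole apparent advantage comes from selection and fitting.

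**6. A less extreme design.** A second simulation forced literature factors into the model, with about 91 to 97 events. The apparent gain was +0.047 to +0.057 and the true gain −0.010 to +0.004. The direction is the same when the model is not built on noise alone.

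**7. Which comparisons are uneven.**

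- SHFM and HFSS come from fixed formulas and carry no fitting optimism here.
- NYHA and INTERMACS are classes without predicted risks. Their calibration needs risks estimated in this cohort, but with few classes the optimism is small.
- Where baseline A and baseline B models are both fitted here, both are optimistic and both need correcting.

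**The case against.** The strongest reply is that this is a detail for the SAP. Section 8.1 defers further detail there, the SAP is not shown, and resampling is commonly specified there. The metrics named in Section 8.3.3 are all proper ones, nothing rules out correction, and the comparison sentence cites a tutorial on prognostic models whose title covers measuring and reducing errors. This stands in part: use of uncorrected same-data values is inferred from the absence of any other sample or step, and is not stated. But the protocol does not leave the comparison open. It fixes the selection threshold, the comparators and the deciding metrics, and followed as written these favour one side. A citation is not a procedure.

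Second, the plan has restraints: literature factors are not chosen from these data, and parsimony limits the model and counts in the comparison. These reduce the optimism but do not remove it, and parsimony has no number attached.

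Third, the size rests on assumptions. That is correct. A gain of zero or below in new patients follows from how the scenarios were built, and Section 1.2.2 gives reasons why existing scores may do poorly in this population. A real gain is possible. The difficulty is that an uncorrected comparison could not tell it from optimism.

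A reader might infer that the new model is bound to look better. The simulations do not support that: it was ahead in 57% of replicates with 120 events and 10 candidates, rising to 99% with 120 events and 40.

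**Conclusion.** The point holds in a limited form. As the protocol is written, the comparison in Section 8.3.3 favours the new model on average, because selection and fitting happen in this cohort and no separate sample or correction is stated. Under the assumed 40 to 120 events and 10 to 40 candidates, the apparent c-index gain is about +0.01 to +0.07 when the true gain is about zero or negative. These ranges are assumptions. Only the ceiling of 120 events follows from the plan, and only for outcomes of the death or VAD kind.

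Two stronger readings are not supported. The documents do not show that uncorrected values will be reported, since the SAP is unseen. Nor does the point undermine the registry: the study summary describes its more specific analyses as hypothesis-generating, the descriptive aims are untouched, and enrolment and data collection do not depend on it. It should be settled before the models are compared and before any claim of improvement is made.

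**What to change.** Amend Section 8.3.3 to state that:

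- the c-index, calibration and accuracy of the new models, and their differences from existing systems, will be corrected for optimism by bootstrap or repeated cross-validation;
- each resample will repeat the whole process: the p<0.10 screen, model building and derivation of the simplified score;
- only corrected values will be used in the comparison with SHFM, HFSS, INTERMACS profile and NYHA class;
- where baseline A and baseline B models are both fitted in this cohort, both will be corrected.

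Shrinkage of the final model is optional. Uniform shrinkage multiplies the linear predictor by a constant, so it improves calibration but leaves the ranking, and hence the c-index, unchanged.

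The cost is computing time and a slightly less favourable reported performance for the new tool. No new data or patient burden is involved. If the SAP already specifies such a correction, one sentence in Section 8.3.3 pointing to it is enough.

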8.4 Modeling of Other Outcomes

The general approach described in Section 8.3 will be used to evaluate the impact of modeled prognosis, self-assessed prognosis, preferences for end-of-life care on the likelihood that a patients considers a VAD implant [objective 2]; the impact of heart failure severity, quality of life, functional limitations and caregiver health status on caregiver burden [objective 3]; the impact of caregiver burden on patient preferences for care and thresholds for considering device implant [objective 3]; and, the impact of pre- and post-VAD therapy or heart transplant on trajectory of caregiver burden [objective 3].

8.5 Health Associated Costs

For Objective 4, health associated costs will be estimated for heart failure subjects in the registry from hospitalizations (days hospitalized, days in the ICU), major cardiac procedures and published data on average costs associated with each. For those subjects enrolled in Medicare fee for service, we will utilize the Medicare Claims (HIC) number to obtain CMS claims data from Medicare Parts A, B and, if purchased by the subject, Part D. The CMS claims data will be obtained for a period beginning one year prior to study enrollment through the end of study follow-up.

8.6 Comparative Analyses of Outcomes

REVIVE-IT registry data will be provided to the INTERMACS study group to be used in comparative analyses of outcomes between patients receiving medical therapy and those receive a VAD [Objective 5]. These analyses will not be performed as part of the REVIVE-IT registry study; rather, they will be performed by the INTERMACS study group. Appropriate consent will be obtained from REVIVE-IT registry participants so that they understand their registry data will be shared with INTERMACS, which is outside of the REVIVE-IT registry study group. Genetic data will not be provided to the INTERMACS study group.

9.0 Data Access, Analysis and Publications

REVIVAL will utilize a Data Access, Analysis and Publications (DAAP) Committee. The DAAP Committee will be responsible for evaluating the scientific merit of proposals, prioritization of proposals and assignment of authorship opportunities. Authorship opportunities will reflect the level of each individual's contribution to the success of the study (i.e., recruitment of subjects, identification of questions for investigation, study design, study leadership, etc.). Further information specific to the composition and activities of this Committee are detailed in the MOP.

10.0 Benefit and Risk Assessment

10.1 Potential Benefit

Data obtained for REVIVAL may provide information to the heart failure subject and his/her doctor regarding prognosis related to heart failure; which has the potential to change the treatments to best match the severity of heart failure.

Medical record information contained within the registry will be used to improve our knowledge and treatment of heart failure and this knowledge may benefit patients with heart failure in the future.

10.2 Potential Risk

All heart failure subjects participating in REVIVAL face risks including, but not limited to the following:

- Cardiopulmonary exercise tolerance test: heart attack, irregular heartbeats, or death in 1 out of 10,000 patients.
- 6MWT and Gait Speed Test: chest pain, shortness of breath, dizziness, fatigue, and falling.
- ECG: localized rash or irritation at the location of electrode placement (rare circumstances)
- Echocardiogram: mild discomfort of the probe touching skin
- Blood draws: fainting, pain, bruising and bleeding at the site of the needle stick and rarely, an infection.
- Biomarker sample collection: breach of confidentiality. Significant precautions will be taken to minimize this risk and prevent disclosure of subject identity to unauthorized individuals.

As with any research study, there may be additional risks that are unknown or unexpected.

In the event of unforeseen or increased risks to subjects, suspension or termination of the clinical study shall be considered (Refer to the MOP for subject management instructions in this event).

11.0 Investigator Responsibility

This clinical study will be performed in accordance with the Declaration of Helsinki, Good Clinical Practice Guidelines, Code of Federal Regulations 45 CFR Parts 46 and 94 and any state laws or local policies, as applicable.

12.0 Institutional Review Board (IRB) Approval

Before implementing this study, the protocol, the proposed informed consent forms and other information to be provided to subjects, must be reviewed by a properly constituted Institutional Review Board and by the DCC.

This study will be carried out in compliance with the protocol and the principles of Good Clinical Practice, as described below:

- ICH Harmonized Tripartite Guideline Guideline for Good Clinical Practice E6(R1), Current Step 4 Version, 10 June 1996.
- US Code of Federal Regulations dealing with protection of human subjects, IRBs and investigator conflicts of interest/research objectivity in clinical studies (including, but not limited to Title 45 Parts 46 and 94).
- Declaration of Helsinki and amendments, concerning medical research in humans (Recommendations Guiding Physicians in Biomedical Research Involving Human subjects).
- IRB local policies, as applicable
- NHLBI policies, as applicable

13.0 Caregiver

The study team member will explain to each heart failure subject's caregiver the nature of the study, its purpose, the procedures involved, the expected duration, the potential risks and benefits involved and any discomfort it may entail. Each caregiver will be informed that participation in the study is voluntary and that if he or she decides not to participate the heart failure subject will still be eligible to participate in the study. Also the caregiver will be informed that he or she may withdraw from the study at any time and that withdrawal of consent will not affect the heart failure subject's participation in the study. This informed consent will be given by means of a standard written statement, written in non-technical language. Alternative methods of providing informed consent information to the caregiver will be allowed per local IRB policies. The caregiver should read and consider the statement before signing and dating it, and should be given a copy of the signed document. If the caregiver cannot read or sign the documents, oral presentation may be made, if witnessed by a person not involved in the study, mentioning to the witness that the caregiver could not read or sign the documents. No caregiver can enter the study before the informed consent has been obtained. The informed consent form is considered to be part of the protocol, and will be submitted for IRB approval in all languages that are approved by the DCC to be used for REVIVAL.

14.0 Subject Data Protection

Demographic information including data points that are considered Personal Identifiable Information (PII) will be collected and managed by the REVIVAL DCC. Access to the data is restricted to protect the privacy of the subject. Only authorized study team members will have access to this data. Data will be collected in accordance with IRB guidelines.

Data will be protected by several measures throughout the life of the study. Paper documents and records will be stored in a secured location with restricted access to authorized personnel

only. Electronic study documents and data will be kept in a password-protected environment, whereby access rights will be terminated at the request of the Site Principal Investigator when study members leave the project.

Protected Health Information (PHI)

PHI will be obtained from the following sources: medical records; any records relating to the condition, treatment received, and response; demographic information; personal identifiers.

The information to be obtained is the minimum necessary to achieve the objectives of the study.

Written HIPAA Authorization will be obtained from all participants with the informed consent process. Data will be linked to study specific identifiers. However, significant identifiers are stored in a separate electronic database table from other data. When the Site Investigator requests user accounts, he or she will specify whether account holders should access all data, or should be restricted from accessing tables with significant identifiers. So, access to identifiers will be limited when appropriate.

